### Figure 1: Study Flow Diagram

### 2 BACKGROUND AND REGISTRY RATIONALE

### 2.1 BACKGROUND

Erectile dysfunction (ED), or impotence, is defined as a persistent failure to develop and maintain erections sufficient for penetrative sexual intercourse. The total prevalence of erectile dysfunction of varying degrees in the United States is estimated to be approximately 30 million. According to the Massachusetts Male Aging Study, an estimated 52% of men over 40 are affected by ED. Prevalence is expected to increase by one-third due to the aging of the population and factors such as increases in weight, dietary changes, smoking behavior, and an emerging increase in diabetes by 2020. Erectile dysfunction is associated with many risk factors or precursors including surgical trauma, diabetes, hypertension, dyslipidemia, and smoking, and has been associated with depression, as well as increased mortality primarily through its association with cardiovascular disease. Following a radical prostatectomy or other acute pelvic surgery or trauma, vascular, neurologic and other tissue injury contributes to ED that is often persistent.

Every man undergoing surgery for prostate cancer will experience some impact on sexual function after prostatectomy, even if erectile function is eventually restored.  Erectile dysfunction also occurs in up to 86% of patients after androgen deprivation therapy, as well as after external beam radiation therapy for prostate cancer.  Restoration of the same degree of potency enjoyed prior to radical prostatectomy (RP) occurs only rarely, and older men and those with decreased pre-operative function generally recover erections less fully than pre-potent and younger men. Nerve sparing surgeries have increased the recovery of post-prostatectomy erectile function by approximately 20% 1-2 years after surgery to over 50% for unilateral and over 75% for bilateral nerve sparing procedures performed by some specialists. However, even with early penile rehabilitation using PDE-5 drug therapy or vacuum erection devices to aid in the restoration of function, only approximately 50-60% of patients will have unassisted functional erections restored by 2 years after prostate cancer treatment.  With almost 200,000 new prostate cancer diagnoses forecast each year in the United States alone, the impact of persistent, prostatectomy-associated ED is great.

Regardless of the cause of ED, the surgical implantation of a penile prosthesis can provide a high level of satisfaction along with durable and reliable restoration of erectile function.  Restoration of erectile function and rigidity can be related to or predictive of improvement in other areas of health that impact quality of life and psychosocial status, as sexual health is integral to overall well-being. 

Although there is a large body of scientific literature describing outcomes associated with penile implants, articles reporting prospectively collected, validated outcomes in large numbers of patients implanted with modern BSC penile implant models are limited.

### 2.2 Registry Design Rationale

The selection of specific effectiveness data measurements in this Registry study was based on outcomes reported in published literature for a range of current ED treatment options, to allow for generalized comparisons between modern, prospective penile prosthesis outcomes and historical data for a variety of ED treatments.

Current recommendations for ED diagnosis, management and research from international evidence-based consensus panels were also consulted to determine which patient-reported outcomes (PROs) are measured as part of the standard of care for clinical evaluation and treatment of ED.

In both clinical practice and research, it has been recommended that ED severity be categorized using the International Index for Erectile Function EF domain (IIEF-EF). The IIEF-5 (also identified as the Sexual Health Inventory for Men or SHIM) is a validated and well established erectile function measure comprised of 5 of the 15 IIEF items, including 4 of the 6 IIEF-EF questions and one question from the intercourse satisfaction domain.  A single-item, validated erection hardness scale/score (EHS) is also commonly recommended and used.  These tools have been successfully employed to measure baseline and post-treatment erectile function and penile rigidity in many clinical trials of ED pharmacotherapy and devices as well as in clinical practice.

For patients with ED due to treatment of prostate cancer, the UCLA Prostate Cancer Index (UCLA-PCI) is a validated 20-item tool for measurement of health-related quality of life specific to sexual, urinary, and bowel function and bother; and has been employed in numerous published studies to demonstrate serial improvements or declines in the six domains commonly affected by prostate cancer treatment.  Each UCLA-PCI domain scale is scored on a scale of 0–100 points with higher values representing better outcomes. A difference of 5–10 points has been considered a clinically important change in a given domain. 

Incontinence or urinary leakage and obstruction often accompanies ED after prostate cancer treatment, at least transiently, and is measured in clinical practice and research using pad counts and weights and validated PROs.  The American Urological Association Symptom Index (AUA-SI) is comprised of 7 of the 8 items of the International Prostate Symptom Score (IPSS), and has been widely used to report baseline and post-treatment clinical urinary symptom outcomes. 

General health-related quality of life (HRQOL) has been evaluated in many different disease state settings with serial assessments using the Short Form Health Survey (SF-12), which is a 12-item adaptation of the RAND 36-Item Health Survey (SF-36) that takes only two to three minutes to complete. The SF-12 (v2) is a practical, reliable, and valid measure of physical and mental health widely used in large population applications. The SF-12v2 is available in multiple modes of administration and in both standard four week and acute one week recall periods. The SF-12 quantifies HRQOL into two composite scores: the Physical Component Summary (PCS) and Mental

Component Summary (MCS) scales. This survey also quantifies HRQOL into the same eight multi-item subscale domains used in the SF-36 with one or two questions in each domain: physical functioning, emotional well-being, general health, pain, energy, social functioning, and role limitations (problems with work or other daily activities) as a result of physical or emotional health. Because this survey uses norm-based scoring, comparisons can be made between published outcomes from the broader SF-36 survey.

Additional measurements were identified for required and optional data collection in the Registry database based on interviews with physician Principal Investigators and their standard of care for management of patients with ED before and after implantation of a penile prosthesis. The two, simple, individual questions about device use and satisfaction with the device were selected based on this feedback and the published studies using similar single-item assessments, since there is no validated tool available at present to measure the outcomes associated with penile implants as a treatment for ED.

The required 1-year follow-up time frame was chosen based on a large body of literature reporting clinical outcomes of this duration or longer after ED treatment, and the recommendations in the labeling for BSC penile prostheses for evaluating long-term device function [AMS 700® with MS Pump Operating Room Manual, 06/10]. The overall 5-year follow-up time frame is the minimum duration that is generally considered long-term follow-up after penile implantation.

### 2.3 DEVICE DESCRIPTION

Devices included in this registry are the AMS 700® Series Inflatable Penile Prosthesis, AMS Ambicor® Penile Prosthesis, and the Spectra™ Concealable Penile Prosthesis. These devices have been approved for marketing and are manufactured by Boston Scientific Corporation (Marlborough, MA, USA). The penile prostheses are intended for use in the treatment of chronic, organic, male erectile dysfunction (impotence). These devices are for men who, after appropriate patient history and diagnostic evaluation as well as discussions with the urologist about other alternative treatment methods, are determined to be suitable candidates for implantation surgery. For specific device descriptions and information about their use and implantation refer to each device's Instructions for Use (IFU) and Operating Room (OR) Manual.

# 2.4 DEVICE ACCOUNTABILITY

All of the BSC devices for which data are being collected in this registry have been approved for marketing, and will be obtained by participating physician investigators through normal purchasing processes. A BSC Patient Information Form (PIF) related to each surgical implant procedure may be completed as per standard practice in addition to entering implant data into the study database. Individual device unit or lot numbers will not be tracked or accounted for in this study.

### 3 REGISTRY OBJECTIVES

#### 3.1 MAIN OBJECTIVE

The objective of this registry study is to prospectively collect data prior to and after BSC penile prosthesis implantation in order to document and evaluate 'real-world' penile prosthetic outcomes including safety, durability, patient satisfaction and effectiveness/Quality of Life.

### 4 REGISTRY DESIGN SUMMARY

The PROPPER Registry is a post-market, multi-center, non-interventional, observational collection of clinical outcomes for patients implanted with a BSC penile prosthesis for the treatment of erectile dysfunction.

As an observational collection, the registry does not dictate patient selection for implantation of BSC devices, and does not direct physicians in the medical and surgical management of patients. Physicians are free to select and manage their patients according to their usual practice. Concomitant urological procedures are allowed and will be recorded. However, outcomes data on these procedures will not be collected, with the exception of select data for any concomitantly implanted AMS 800 Artificial Urinary Sphincters or AdVance slings for the treatment of incontinence.

BSC recommends that all devices are implanted according to the device specific Instruction for Use (IFU) and/or Operating Room (OR) manuals and the site or physician's standard of care.

Patient data will be collected from the baseline/pre-operative visit, the procedure, and follow up evaluations which will occur according to each physician's standard of care, up to 5 years post-operatively. A 1=year follow up evaluation will be required, and a 2-year follow-up evaluation will be strongly encouraged. Follow-up evaluations may occur during visits with the physician and/or by telephone or mail.

Each physician will determine if the device implantation procedure was successful based on his/her standard of care. Any reported intra-operative complications will be collected in the registry database. Success will be measured post-operatively by querying patients about device use.

The PROPPER Registry is designed to obtain post market safety and effectiveness information as well as to serve as an active surveillance system for collecting device related events or complications and malfunctions in patients implanted with BSC penile prostheses and reporting product complaints to BSC. This will provide a robust database of clinical information from which a number of analyses can be performed.

# 5 PATIENT ELIGIBILITY

The PROPPER Registry is expected to enroll approximately 500 to 1500 patients at up to 16 sites throughout the US and Canada. Enrollment is expected to be over a one to two year period with up to five year patient follow-up.

### 5.1 INCLUSION CRITERIA

Men diagnosed with erectile dysfunction (ED) for whom a BSC penile prosthesis is recommended by their physician are eligible for inclusion. Potentially eligible men should also meet the following inclusion criteria for study enrollment:

- Willing and able to provide written informed consent prior to enrollment (if applicable)
- Willing to be seen or contacted by phone by the physician and answer at least 2 questions related to satisfaction, device use, and potential issues with the device 1 year following implantation of an BSC penile prosthesis, as well as standard physician assessments throughout the study

### 5.2 EXCLUSION CRITERIA

Men who are deemed by their physician to be not suitable for a penile implant will be excluded.

### 6 PATIENT ENROLLMENT

All patients who meet eligibility criteria should be encouraged to enroll in the registry. Patients will be considered enrolled once they have signed an informed consent. If a site has a waiver of informed consent each patient from that site will be considered enrolled once the first data records are entered into the database. A unique patient identifier will be assigned to each patient at enrollment (upon signing an ICF or database entry). The PROPPER Registry is expected to enroll approximately 500 to 1500 patients at up to 16 sites throughout the US and Canada. Enrollment is expected to be over a one to two year period with up to five year patient follow-up. A total of more than 500 patients are anticipated to be implanted and entered into the registry database per year of enrollment. Based on historical estimates and assuming 10 to 15 participating physicians, the following number of each BSC penile prosthesis type will be implanted each year of enrollment: 500 AMS 700® Inflatable Penile Prostheses, 15 AMS Ambicor® Penile Prostheses, and 20Spectra™ Concealable Penile Prostheses.

### 7 DATA COLLECTION

Data will be collected via internet-based electronic data capture (EDC) with paper based questionnaires for collection of patient-reported outcomes (PRO) data. The PRO data will be entered into the registry database by the physician, physician staff or BSC staff. The EDC module will be developed and maintained by BSC.

Physicians are not required to complete all data fields in the database. Each will be asked to enter the required data at baseline/procedure and one-year follow-up for each

patient and optional data based on the information that they collect per their own standard of care.

Additional outcomes will be collected at whatever time frames are deemed appropriate by the physician, based on their standard of care for treatment of ED.

This is an observational collection of prospective patient data, with the following data required for each enrolled physician and patient:

- basic practice information for each physician
- baseline/pre-operative patient information: age, race/ethnicity, primary etiology of ED, relevant concomitant medical conditions and concomitant medications that might impact ED
- implantation surgery data: date of procedure, surgical approach, implant model type, drain, dressing, concurrent procedures, significant corporal fibrosis or scarring noted, curvature correction procedure(s) (e.g., for Peyronie's disease), and patient status post-op
- 1-year post-operative follow-up (at a minimum): each patient is asked 3 standardized questions during a visit or by phone to record any potential device related complications and their outcomes, patient satisfaction with implanted device(s) and use of device.

Refer to Table 1 for the study data collection schedule.

### 7.1 DEVICE USE AND SATISFACTION QUESTIONS

The following two standardized, non-validated questions will be used to assess postimplantation patient satisfaction with the device and use of the device:

- How satisfied are you with the device(s)? (5-point scale)
  - 1 Very Dissatisfied
  - 2 Dissatisfied
  - 3 Neither Satisfied nor Dissatisfied
  - 4 Satisfied
  - 5 Very Satisfied
- Are you using the device? (Y/N)
  - (If yes) How often are you using the device? (less than once per month, or more than once per month)
  - How many times per month?
  - If no, why aren't you using the device? (Loss of partner, partner disinterest, device problem, device dissatisfaction, health decline, other, other device use reason)
  - If yes, and not using the device as often as desired, or if dissatisfied with the device, indicate why (Loss of partner, partner disinterest, device problem, device dissatisfaction, health decline, other, other device use reason)

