- Query for any device related complications and their outcomes by asking patients if they have had any surgery on their penis or problems with the device since their penile prosthesis was implanted (Y/N)
- Patients will be asked:
  - How satisfied they are with the device(s) (using a 5-point scale)

- If they are using the device (Y/N)
  - If yes, how often they are using the device (less than once per month or more than once per month)
     *o* How many times per month?
  - If no, why aren't you using the device (loss of partner, partner disinterest, device problem, device dissatisfaction, health decline, other – describe, other device use reason).
  - If yes, and not using the device as often as desired, or if dissatisfied with the device, indicate why ((loss of partner, partner disinterest, device problem, device dissatisfaction, health decline, other – describe, other device use reason).
- Number of pads used daily (if incontinence indicated pre-operatively)
- Pad weight (24-hour test) (if incontinence indicated pre-operatively)
- Penile length measurement with device fully inflated (measured from suprapubic fat pad to tip)
- Penile girth measurement with device fully inflated (circumference measured 1cm proximal to the proximal end of the corona)
- Stretched penile length measurement with device deflated (measured from suprapubic fat pad to tip)
- Patient query any office visits in past year for treatment of depression Y/N
  - o If Yes: approximately how many visits
  - If Yes: taking any depression medication
- Effectiveness/quality of life assessments

Patient questionnaires to measure effectiveness will be optional at baseline and at all follow-up visits. Included are the following validated, patient-reported outcome questionnaires:

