#### *Recommended for all patients with post-prostatectomy ED or incontinence:*

- AUA-SI/IPSS urinary symptom questionnaire
- UCLA-PCI urinary, sexual and bowel function and bother questionnaire

Any reported intra-operative or post-operative device or surgery related complications will be recorded throughout study follow-up (for BSC products only). This information will include:

- Complication
- Treatment
- Location of treatment

• Resolution (Resolved or Continuing) Potential device or surgery related complications are described in the device specific IFU and OR manuals.

Up to 1500 patients with erectile dysfunction (ED) electing to receive a BSC penile prosthesis implant will be included in this registry.

Analyses of multi-center data for initial publication(s) may be performed after approximately 500 patients complete 1 year follow-up. Additional individual and multi-center data analyses may be performed as warranted throughout the study for publication(s). Analysis for multi-center publication(s) is planned after the study enrollment is complete and all the enrolled patients have completed their one-year and five-year follow-up evaluations, consistent with each physician's standard of care.

Continuous variables will be presented as mean +/- SD; ordinal variables will be summarized using median with interquartile ranges; categorical variables will be presented as count and proportion.

Kaplan-Meier method will be used to estimate the event rate over time by device type for major complications.

For within-patient change at 1 year follow up compared to the baseline visit, signed rank test or paired t-test may be used for continuous variables and McNemar's test may be used for binary variables when applicable. Mixed effects model or Generalized Estimating Equation model may be used to estimate the change from baseline across follow up

Safety/Device Malfunction Assessments:

Statistical Analyses, Including Determination of Sample Size: visits when appropriate.

The data to be collected in electronic data forms will include the following:

Table 1: Electronic	; data	collection	schedule
---------------------	--------	------------	----------

Data	Baseline/ Procedure	Interim Follow-Up*	1 Year Follow-Up*	2 - 5 Year (Annual) Follow-Up*
Date of Informed Consent/first data record	R			
Demographics and Characteristics	R			
ED History	R			
Depression History	0	N/A	0	0
Implantation Procedure Details	R			
Device Use and Satisfaction	N/A	0	R	SE

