#### Endpoint:

- How satisfied are you with the device(s)? (5-point scale)
  - 1 Very Dissatisfied
  - 2 Dissatisfied
  - 3 Equally Satisfied and Dissatisfied
  - 4 Satisfied
  - 5 Very Satisfied
- Are you using the device? (Y/N)
  - (If yes) How often are you using the device? (less than once per month, or more than once per month)
  - How many times per month?
  - If no, why aren't you using the device? (Loss of partner, partner disinterest, device problem, device dissatisfaction, health decline, other, other device use reason)
  - If yes, and not using the device as often as desired, or if dissatisfied with the device, indicate why (Loss of partner, partner disinterest, device problem, device dissatisfaction, health decline, other, other device use reason)

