#### Statistical Analysis:

The number and percentage of patients with responses in each category for the satisfaction and the device use questions at 1-year visit and any of the additional followup time points with data available will be summarized for each device type and overall for all BSC penile prostheses recipients.

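### The use-frequency item has no option for exactly once a month, and Section 8.3.1 does not say that the recorded count decides the category

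*Combined protocol and SAP*

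**What the plan says.** Section 7.1 puts a yes/no question on device use and then asks users "How often are you using the device? (less than once per month, or more than once per month". The next line asks "How many times per month". The synopsis has the same pair of options: "If yes, how often they are using the device (less than once per month or more than once per month". The endpoint list in Section 8.3.1 repeats them ("less than once per month, or more than once per month") and also includes the count.

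The Section 8.3.1 analysis will summarise "The number and percentage of patients with responses in each category for the satisfaction and the device use questions at 1-year visit" and at other time points with data, by device type and overall. It gives no rule for a man at exactly once a month and none for a tick-box that conflicts with the count.

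Table 1 marks the row "Device Use and Satisfaction" as required at 1 year, optional at interim visits and strongly encouraged in years 2 to 5. Section 7 says that at 1 year "each patient is asked 3 standardized questions during a visit or by phone", use of the device being one of the three topics. Neither place marks the frequency sub-item or the count separately as required.

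**The concern.** A response set should give every respondent one correct answer. Here a man who uses the device once a month has none. He may tick the lower option, tick the upper option or leave the item blank. Section 4 allows follow-up by visit, telephone or mail, so different sites or patients could resolve the same answer differently.

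What is at stake is limited to the frequency split among users, one descriptive component of Effectiveness Objective 1. The boundary between the two reported categories would not have a fixed meaning, and the denominator could lose men who left the item blank.

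**Working it through.** The plan attaches no figure to this item, so there is nothing to reproduce. The check has two parts: whether the options are exhaustive, and how far the reported split could move.

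**Are the options exhaustive?** Let x be uses per month among men who say they use the device. The synopsis, Section 7.1 and Section 8.3.1 all offer {x < 1} and {x > 1}. Their union omits x = 1. Because the wording agrees in all three places, it is not a slip in a single section.

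**Does the analysis close the gap?** The count can record x = 1 and is part of the listed endpoint. The analysis paragraph tabulates responses by category and does not link the two items. Section 7 also says that physicians need not complete every data field, so the count may be missing for some men.

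**How far can the split move?** Among responding users, let b, q and a be the shares with x < 1, x = 1 and x > 1, so b + q + a = 1. The reported share in the upper category is:

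- a, if all men at x = 1 tick the lower option;
- a + q, if they all tick the upper option;
- a/(1 − q), if they all leave it blank. This lies between a and a + q, because a ≤ 1 − q.

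The full range is (a + q) − a = q.

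The documents give no value for q. As an assumption, for illustration only, per 100 responding users:

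| q | Men at exactly once a month | Largest movement of the split | Denominator if all left blank |
|---|---|---|---|
| 5% | 5 | 5 points | 95 |
| 10% | 10 | 10 points | 90 |
| 20% | 20 | 20 points | 80 |

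**Small device groups.** Section 8.1 contemplates analyses of 10 to 25 patients for some newer devices. One man moved between categories shifts the split by 1/u, where u is the number of responding users. Since u cannot exceed the number of patients, the shift is at least 1/25 = 4 points in a group of 25 and at least 1/10 = 10 points in a group of 10.

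**After the fix.** If the category is derived from a completed count with a split at x < 1 versus x ≥ 1, every user has a category and the unclassifiable share falls from q to 0.

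**The case against.** The strongest reply is that the plan already collects what is needed. The count follows the two-option item in all three places and belongs to the endpoint. Section 8.3.1 speaks of the device use questions in the plural, so nothing prevents the analyst from tabulating the count or deriving the category from it. Where the count is complete and used, the error is zero. This stands, and it makes misclassification possible rather than certain. It does not remove the gap: a two-category table produced as written still has no rule for these men.

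Stronger readings are tempting, but the documents do not support them:

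- A reader might infer that a required question is defective. The requirement attaches to the use and satisfaction block at 1 year, and the frequency sub-item is not separately marked.
- A reader might infer that the registry's measure of success is compromised. Section 4 measures success by asking about device use, and the synopsis adds satisfaction. Neither sets a threshold at once a month, and no hypothesis or target rests on the split.
- A reader might turn q into a headcount by applying it to the 500 + 15 + 20 = 535 implants expected per enrollment year. That is the wrong denominator, because the item is asked only of men who have follow-up and report using the device.

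**Conclusion.** The point holds in a narrow form. The response options omit exactly once a month, and the analysis text does not say that the adjacent count fills the gap. Men at that frequency can be misclassified or dropped from the frequency split. The split can move by up to q, their share of responding users, which the documents do not give. The bound assumes that the other users tick correctly and that the count is not used. The yes/no use item and the satisfaction item are unaffected. This is a minor flaw in one descriptive sub-item, worth correcting because the remedy is cheap.

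**What to change.** In Section 8.3.1, add a rule that the category is derived from the recorded count as fewer than one versus one or more uses per month. The count prevails where it conflicts with the tick-box. The tick-box is used only when the count is missing, and the number of men classified that way is reported.

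Going forward, reword the options in the synopsis, Section 7.1 and Section 8.3.1 to *less than once per month* and *once per month or more*.

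The cost is one derivation rule and a small form change. There are two limits. If data have already been collected, two versions of the tick-box will coexist and should be identified in the dataset. Earlier once-a-month answers with no count also cannot be recognised. Those ticked upward happen to fall on the right side of the new split, while those ticked downward or left blank stay unresolved.
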